### 7.3.1 Primary analyses

The primary analysis will be performed on the FAS [observed cases (OC)]. Mean changes from baseline in HbA1c after 24 weeks of treatments will be analysed using a restricted maximum likelihood-based repeated measures approach. Analyses will include the fixed, categorical effects of baseline insulin dose, treatment, week, and treatment by week interaction, as well as the continuous, fixed covariates of baseline HbA1c and baseline HbA1c by week interaction. An unstructured (co)variance structure will be used to model the within patient measurements.

If this analysis fails to converge, the following covariance structures will be tested: Toeplitz, AR (1), and compound symmetry. The (co)variance structure converging to the best fit, as determined by Akaike's information criterion, will be used as the primary analysis. The Kenward-Roger approximation will be used to estimate denominator degrees of freedom. Significance tests will be based on least-squares means using a two-sided  $\alpha = 0.05$  [two-sided 95% confidence intervals (CI)]. **The residuals are assumed to have a multivariate normal distribution with zero means and covariance matrix as mentioned above.** All analyses will be implemented using SAS®. The primary treatment comparisons will be the contrast between treatments at Week 24.

The statistical model will be:

HbA1c change from baseline = overall mean + baseline HbA1c + baseline insulin dose  
+ treatment + week + week by baseline HbA1c interaction  
+ week by treatment interaction + random error

Proprietary confidential information.

© 2015 Boehringer Ingelheim International GmbH or one or more of its affiliated companies. All rights reserved.

This document may not - in full or in part - be passed on, reproduced, published or otherwise used without prior written permission.

secondary and certain other endpoints (to be specified in TSAP) to obtain the odds ratio between treatment groups and its 95% CI and 2-sided p-value.

- [REDACTED]
- [REDACTED]

For these analyses, patients will be assigned to the treatment they were randomised to.

The analysis of endpoints related to questionnaires will be described in the TSAP.

### 7.3.3 Safety analyses

All safety data will be displayed and analysed using descriptive statistical methods. Depending on the character of the individual safety endpoint, the most appropriate way to summarize the results as frequency tables for categorical data or descriptive statistics for continuous data will be used. No formal inferential analysis is planned for safety comparison.

AEs will be coded using the Medical Dictionary for Drug Regulatory Activities (MedDRA) coding dictionary. All events with an onset after the first dose of study medication up to a period of seven days after the last dose of study medication will be assigned to the treatment phase for evaluation. This includes AEs that start before first study medication intake and deteriorate under treatment. Other AEs will be assigned either to the screening, run-in, or follow-up phase as appropriate. Safety analyses will be performed on the TS, with patients assigned to the treatment they were randomised to. Additional listings based on actual treatment at onset of AE will be produced for patients who receive incorrect treatment at any point throughout the trial.

Laboratory values taken after the first dose of randomised treatment up to a period of seven days after the last intake of treatment will be assigned to the treatment phase for evaluation. Laboratory values will be compared to their reference ranges and frequency tables will be provided for the number of patients within and outside the reference range.

Changes from baseline in blood pressure and pulse rate will be summarised by treatment group.

Further details on the safety analysis will be specified in the TSAP.

#### 7.3.4 Interim analyses

No interim analysis is planned for this trial.

#### 7.3.5 Pharmacokinetic analyses

No pharmacokinetic sampling is planned for this trial.

#### 7.3.6 Pharmacodynamic analyses

No pharmacodynamic analysis is planned for this trial.

### 7.4 HANDLING OF MISSING DATA

#### 7.4.1 Efficacy endpoints

In the primary analysis, if a patient misses a visit, the missing data will not be imputed. The mixed effect model will handle missing data based on a likelihood method under the "missing at random assumption". Following the intention-to-treat (ITT) principle, every randomised patient with at least baseline and one on-treatment measurement will be included in the analysis.

If rescue therapy is initiated, HbA1c and FPG values after rescue will be set to missing and the missing data handled as above (OC or LOCF), according to the analysis strategy.

**For the analysis of hypoglycaemia endpoints, the available data of all patients in the TS will be analysed (OC approach) and no imputation performed.**

For binary endpoints including an HbA1c response criterion, non-completer's considered failures (NCF) approach will be used, i.e., patients who discontinue from the trial prematurely and have no Week 24 HbA1c value will be considered as non-responders.

Methods to handle any other exceptional cases will be considered before unblinding the data and will be applied in a manner consistent with other trials of this type. The evaluability of patients with deviations from the protocol likely to confound the treatment response will be decided prior to unblinding.

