**A total of 300 patients will be randomised.**

Proprietary confidential information.

© 2015 Boehringer Ingelheim International GmbH or one or more of its affiliated companies. All rights reserved.

This document may not - in full or in part - be passed on, reproduced, published or otherwise used without prior written permission.

Based on pooled data from the 1218.36 and 1218.63 trials [REDACTED] assuming a standard deviation of 1.2% in both groups in the FAS with a 0.77% difference in HbA1c change from baseline in treatments, a number of 150 patients in each treatment arm will show superiority with a power >99%. This determination of power is based on a Student's t-test and a two-sided significance level of 5%.

Software package nQuery version 7.0 was used to derive the sample size.

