6.3 PATIENT SETS ANALYSED

- **Randomised set (RS):**
This patient set includes all randomised patients, whether treated or not.
- **Treated set (TS):**
This patient set includes all patients who were dispensed study medication and were documented to have taken at least one dose of investigational treatment.
- **Full analysis set (FAS):**
This patient set includes all patients randomised in the TS who have a baseline and at least one on-treatment HbA_{1c} value.
- **FAS-completers-24 (FASC24):**
This patient set includes all patients in the FAS who complete a minimum treatment duration of 149 days, did not prematurely discontinue the trial and have an available HbA_{1c} measurement within the time window for the Week 24 visit (Visit 98 for non-Japanese and Visit 7 for Japanese patients up to day 176). This analysis set is not required for the analysis at Week 52. See [Table 6.7: 1](#).
- **Per protocol set (PPS):**
This patient set includes all patients in the FAS who do not have any IPVs relating to efficacy, cf. [Table 6.2: 1](#).

Table 6.3: 1 Patient sets analysed

Class of endpoint	Patient set			
	TS	FAS	PPS	FASC24
Primary endpoint		Primary analysis	Sensitivity analysis	Sensitivity analysis
Secondary and further endpoints		X		
Safety endpoints	X			
Demographics	X			
Baseline efficacy variables		X		

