Baseline values will not be carried forward in general, but can be used for interpolation. Only for patients with rescue medication before the first on-treatment HbA_{1c} measurement, baseline HbA_{1c} values will be used to replace values after the start of rescue medication.

Missing values within a course of measurements on treatment will be interpolated based on the last observed value before the missing visit and the first observed value after the missing visit. This is independent from the selection of a value as the picked visit value (cf. [Section 6.7](#)) to be used in the descriptive analysis by visit. Replacement of missing values will only be performed for visits up to the planned visit to be reached by all randomised patients in the trial.

Interpolation will be done according to the formula described below:

Let: D_0 = date of a visit with a missing endpoint value;

D_1 = date of the next-visit (with end-point value non-missing) after the visit with missing endpoint;

D_{-1} = date of a previous-visit (with end-point value non-missing) before the visit with missing endpoint;

E_i = endpoint value for visits D_i for $i = -1, 0, 1$.

Then the missing endpoint value can be interpolated as:

$$E_0 = E_{-1} + \left((E_1 - E_{-1}) \times \frac{D_0 - D_{-1}}{D_1 - D_{-1}} \right).$$

Multiple imputation (MI)

A multiple imputation approach will be used as a sensitivity analysis for the primary endpoint. Further details can be found in [Section 7.4.2](#).

Non-completers considered failure (NCF)

For binary endpoints like a treat to target response of $HbA_{1c} < 7.0\%$ a conservative method to replace missing values is to consider them as “failures”. Missing data due to early discontinuation will be replaced as “failure” (e.g. $HbA_{1c} \geq 7.0\%$) up to the planned final visit to be reached by all patients. Similarly, values obtained after the start of rescue therapy will be considered “failure”.

For binary endpoints that are derived from quantitative endpoints (e.g. HbA_{1c}), missing values within a course of measurements on treatment will be replaced on the basis of the corresponding imputed value of the underlying quantitative endpoint (e.g. based on imputation as described for HbA_{1c}).

Table 6.6: 1 Summary of imputation methods for efficacy endpoints

Imputation method	Endpoint	Handling of missing values	Handling of values after rescue therapy

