7.5.2 Secondary endpoints

Proportion of patients with at least one hypoglycaemia accompanied by a glucose value during 24 weeks of treatment

Logistic regression for the proportion of patients experiencing at least one hypoglycaemia after 24 weeks will be performed on the FAS (OC); all on-treatment hypoglycaemias will be considered:

- up to drug stop date if a patient prematurely discontinues (Japanese patients that prematurely discontinue prior or at day 175)

- up to trial medication stop date – 1 if a non-Japanese patient does not prematurely discontinue
- up to day 175 if a Japanese patient does not prematurely discontinue prior day 176.

The model will include *treatment* as fixed effect and *baseline HbA_{1c}* and *baseline daily basal insulin dose* as linear covariates.

Frequencies regarding the number and percentage of patients experiencing at least one hypoglycaemia accompanied by a glucose value during 24 weeks in each treatment group will also be presented based on FAS(OC) .

Proportion of patients with HbA_{1c} on treatment <8.0% after 24 weeks of treatment

Logistic regression for the patients achieving HbA_{1c} <8.0% at Week 24 will be performed on FAS (NCF); patients who do not complete 24 weeks of treatment will be considered non-responders. The model will include *treatment* as fixed effect and *baseline HbA_{1c}* and *baseline daily basal insulin dose* as linear covariates. Patients with baseline HbA_{1c} <8.0% will be excluded from the analysis.

A frequency table with the number and percentage of patients with HbA_{1c} <8.0% at Week 24 in each treatment group will be also be presented based on FAS (NCF).

Proportion of patients with HbA_{1c} on treatment <7.0% after 24 weeks of treatment

Logistic regression for the patients achieving HbA_{1c} <7.0% at Week 24 will be performed on FAS (NCF); patients who do not complete 24 weeks of treatment will be considered non-responders. The model will include *treatment* as fixed effect and *baseline HbA_{1c}* and *baseline daily basal insulin dose* as linear covariates. Patients with baseline HbA_{1c} <7.0% will be excluded from the analysis.

Frequencies regarding the number and percentage of patients with HbA_{1c} <7.0% at Week 24 in each treatment group will be also be presented based on FAS (NCF).

Proportion of patients with HbA_{1c} lowering by at least 0.5% after 24 weeks of treatment

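### The HbA1c responder analyses count non-completers as failures but run on a set that drops treated patients with no on-treatment HbA1c

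*Protocol*

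**What the plan says.** **Failure rule.** Protocol 7.4.1 makes non-responders of patients who leave early and lack a Week 24 HbA1c. SAP 6.6 says of such binary endpoints: "Missing data due to early discontinuation will be replaced as" failure, and Table 6.6: 1 repeats this. SAP 7.5.2 applies it to all three responder endpoints (HbA1c below 8.0%, below 7.0%, and a fall of at least 0.5%): "patients who do not complete 24 weeks of treatment will be considered non-responders". None of these places makes an exception for a patient with no post-baseline value.

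**Analysis set.** SAP 7.5.2 runs both the logistic models and the frequency tables on FAS (NCF). SAP 6.3 defines the FAS: "This patient set includes all patients randomised in the TS who have a baseline and at least one on-treatment" HbA1c value. Protocol 7.3 sets the same condition, and Table 6.3: 1 assigns secondary endpoints to the FAS only. For the primary mixed model, Protocol 7.4.1 says that "every randomised patient with at least baseline and one on-treatment measurement will be included in the analysis".

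**Denominator.** SAP 7 takes percentages over every patient in the relevant set, whether or not the value is missing. Set membership therefore decides the rate.

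**The concern.** For the mixed model (MMRM) the FAS condition does no harm, because a patient with no post-baseline HbA1c adds nothing to the likelihood. A responder analysis with non-completers as failures is different. The same patient has a defined outcome, failure, and removing that patient discards a known zero from the numerator side and one from the denominator.

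Any such patients raise the reported responder rate in their arm. If they are more frequent in one arm, the treatment comparison is shifted by an exclusion that depends on what happened after randomisation. SAP 6.6 chooses the failure rule because it is conservative; this exclusion works against that aim.

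**Working it through.** **1. The plan's own figure.** The only sample-size figure is for the primary endpoint: "a number of 150 patients in each treatment arm will show superiority with a power >99"%, "assuming a standard deviation of 1.2% in both groups in the FAS", "with a 0.77% difference in" HbA1c change, using "a Student's t-test and a two-sided significance level of 5"%. The noncentrality is 0.77 / (1.2 × √(2/150)) = 5.56 on 298 degrees of freedom, which gives power 0.9998. The stated figure reproduces. With 10% of each arm outside the FAS (135 per arm) power is still 0.9995. The primary endpoint is not at issue, and no figure is given for the responder endpoints.

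**2. Who is lost.**
- The flow chart schedules the first post-baseline HbA1c at Week 6 (Day 43).
- A patient who stops before then should have Visit 98 as soon as possible (Protocol 3.3.4.1 and 6.2.2), and the flow chart includes HbA1c at that visit.
- SAP 6.7 counts an HbA1c as on-treatment up to 7 days after drug stop.
- Visit 98 within 7 days: the patient is in the FAS and is counted as a failure, as intended.
- Visit 98 later than 7 days, or missed: no on-treatment HbA1c exists, so the patient is out of the FAS.
- Protocol 4.3 discontinues patients after 10 consecutive days without study medication and then calls them for Visit 98. Counted from the last dose taken, that visit already lies beyond 7 days. If this happens before the Week 6 sample, the patient leaves the FAS despite attending.

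**3. Size.** No early-loss rate or expected responder rate appears in the visible text, so both are assumed here. Let r be the responder rate among all treated patients with the lost patients as failures, and e the share of the arm lost. Then

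FAS rate = r / (1 − e), and FAS odds = r / (1 − e − r).

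Take r = 0.30 for placebo and 0.50 for linagliptin: difference 20.0 points, odds ratio (0.50/0.50) / (0.30/0.70) = 2.33.

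| Loss, placebo / linagliptin | FAS rates | Difference | Odds ratio |
|---|---|---|---|
| 2% / 2% | 0.30/0.98 = 30.6%; 0.50/0.98 = 51.0% | 20.4 | (0.50/0.48)/(0.30/0.68) = 2.36 |
| 2% / 5% | 30.6%; 0.50/0.95 = 52.6% | 22.0 | (0.50/0.45)/(0.30/0.68) = 2.52 |
| 5% / 2% | 0.30/0.95 = 31.6%; 51.0% | 19.4 | (0.50/0.48)/(0.30/0.65) = 2.26 |

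With 150 per arm, 2% is 3 patients and 5% is 7 or 8.

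**4. A more extreme case, from the reported side.** Suppose the FAS shows 50% against 30% with 10% lost on linagliptin and 2% on placebo. Restoring the lost patients as failures gives 0.50 × 0.90 = 45.0% and 0.30 × 0.98 = 29.4%, a difference of 15.6 instead of 20.0 points. A shift of about 4 points thus needs a marked imbalance in early loss.

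**The case against.** The best defence is that FAS (NCF) openly names a set and an imputation rule to be applied within it. The protocol and SAP define the FAS alike, so there is no conflict between them. That is fair as a description, but the failure rule itself is worded without that limit, and no visible text restores the patients left out.

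A second defence concerns the route out. Withdrawal for lack of efficacy presupposes hyperglycaemia uncontrolled on rescue medication (Protocol 3.3.4.1). Rescue medication starts no earlier than Visit 4, and an HbA1c is taken beforehand unless a recent one exists (Protocol 4.2.1). Patients removed for that reason should normally already have an on-treatment HbA1c. This stands. The remaining routes are voluntary withdrawal, early intolerance and the 10-day rule, and the documents give no reason to expect a particular imbalance between arms.

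Three stronger readings are tempting and are not supported:
- That the plan breaks an intention-to-treat claim made for the responder endpoints. That sentence closes the paragraph on the primary analysis and states its own condition; the failure rule comes later and carries no such claim.
- That all the earliest non-completers are dropped. Those with an HbA1c within 7 days of stopping are kept and counted as failures.
- That the responder rates are known to be inflated. This depends on early losses for which the documents give no rate.

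Protocol 7.3.2 is only partly visible and parts of the SAP are redacted, so a supplementary responder analysis on a wider set may exist. None can be seen.

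**Conclusion.** The gap is real but narrow. For treated patients who stop before the Week 6 sample and have no HbA1c within 7 days of drug stop, the failure rule is stated but not carried out. For all other non-completers in the FAS it works as written.

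On the assumed rates of 30% and 50%, equal 2% loss moves the difference by 0.4 points, and 2% against 5% moves it by −0.6 to +2.0 points. Direction and size in this trial cannot be fixed from the documents. Only secondary endpoints are touched, SAP 5.2.1 names no key secondary endpoint, and the primary result and its power do not change. Severity: minor.

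**What to change.** In SAP 6.3 and 7.5.2, run the three responder logistic models and frequency tables on all treated patients with a baseline HbA1c. Count those with no on-treatment HbA1c as failures and report their number per arm. Keep the planned exclusions from the models of patients already below 8.0% or 7.0% at baseline. Keep the FAS for the MMRM.

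The cost is SAP wording and one change of analysis set. The model covariates are baseline values, so no new data are needed. Responder rates will be slightly lower. The set would still omit patients randomised but never treated, so it should not be described as all randomised patients.

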#### 7.4.2 Safety and other endpoints

With respect to safety evaluations, it is not planned to impute missing values.

The handling of missing [REDACTED] as patient reported outcome measures data will be specified in the TSAP or a separate health economics analysis plan, as appropriate.

#### 7.5 RANDOMISATION

The sponsor will arrange for the randomisation as well as packaging and labelling of study medication. Eligible patients will be randomly assigned to one of the two treatment groups, with equal allocation of treatments. The randomisation list will be generated using a validated system, which involves a pseudo-random number generator so that the resulting treatment sequence will be both reproducible and non-predictable.

The randomisation will be stratified by HbA1c (< 8.5% vs. ≥ 8.5%) as determined from the blood sample taken at Visit 1 and insulin dose (< 40 international units total daily dose vs. ≥ 40 international units total daily dose) as determined at the beginning of the placebo run-in period (Visit 2). To ensure appropriate representation of patients with insulin doses of < 40 international units total daily dose as well as ≥ 40 international units total daily dose, the trial team will monitor the proportion of patients being recruited into these categories. The limitation of recruitment of a particular category may be arranged (on trial level and/or country level).

The allocation process will be performed at Visit 3 through IRT. However, the IRT allocation and randomization will not increase the study medication bottles at each trial site based on stratification.

Access to the code will be restricted to dedicated randomisation personnel and any exceptional access to the code (in case of an emergency) will be documented according to the sponsor's SOPs.

The trial will only be unblinded after all eCRF and electronic data have been entered into the trial database, after queries have been resolved, and after the database has been locked. Access to the codes will be controlled and documented by a signed confidentiality statement, which will be stored in the TMF.

Practical aspects of the treatment allocation process and methods to carry out blinding are detailed in [Sections 4.1.2](#) and [4.1.5](#), respectively.

#### 7.6 DETERMINATION OF SAMPLE SIZE

**This trial will be powered to detect differences between linagliptin and placebo in HbA1c change from baseline after 24 weeks.**

**A total of 300 patients will be randomised.**

Proprietary confidential information.

© 2015 Boehringer Ingelheim International GmbH or one or more of its affiliated companies. All rights reserved.

This document may not - in full or in part - be passed on, reproduced, published or otherwise used without prior written permission.

Based on pooled data from the 1218.36 and 1218.63 trials [REDACTED] assuming a standard deviation of 1.2% in both groups in the FAS with a 0.77% difference in HbA1c change from baseline in treatments, a number of 150 patients in each treatment arm will show superiority with a power >99%. This determination of power is based on a Student's t-test and a two-sided significance level of 5%.

Software package nQuery version 7.0 was used to derive the sample size.

## 8. INFORMED CONSENT, DATA PROTECTION, TRIAL RECORDS

The trial will be carried out in compliance with the protocol, the principles laid down in the Declaration of Helsinki, in accordance with the ICH Harmonised Tripartite Guideline for GCP and relevant BI SOPs. Standard medical care (prophylactic, diagnostic and therapeutic procedures) remains in the responsibility of the treating physician of the patient.

The investigator should inform the sponsor immediately of any urgent safety measures taken to protect the study subjects against any immediate hazard, and also of any serious breaches of the protocol/ICH GCP.

*For Japan:*

*The investigator should inform the sponsor immediately of any urgent safety measures taken to protect the study subjects against any immediate hazard, and also of any serious breaches of the protocol, ICH GCP, and the Japanese GCP regulations (Ministry of Health and Welfare Ordinance No. 28, March 27, 1997).*

The rights of the investigator and of the sponsor with regard to publication of the results of this trial are described in the investigator contract. As a general rule, no trial results should be published prior to finalisation of the Clinical Trial Report.

*For countries with insurance cover requirements:*

*Insurance Cover: The terms and conditions of the insurance cover are made available to the investigator and the patients via documentation in the ISF.*

